9. STUDY CONDUCT

9.1 Schedule of Assessments

The schedule of assessments is shown in months, as it facilitates better comprehension, preventing potential errors, in the interpretation of the exact timing for each assessment. On the other hand, in order to facilitate integration with the weekly-based schedule of ECP, and also budget considerations, we use the following transformation between weeks and months when addressing the schedule of assessments:

- a- 3 months: Week 12 \pm 2 week
- b- 6 months: Week 24 \pm 2week
- c- 9 months: Week 36 \pm 2 week
- d- 12 months or 1 year: Week 52 \pm 1 month

The schedule of assessments is shown in Table 2.

Table 2: Schedule of Assessments

Procedures	Screening (-30days)	Baseline ⁵ (Week 2)	Month 3	Month 6	Month 9	12 months/1year	Til End of Study (every 3 months through 2 years) ⁸
Informed Consent	X						
Inclusion/Exclusion Criteria	X						
Vital Signs		X	X	X	X	X	
Medical History/ Interim History ¹	X	X	X	X	X	X	
Physical Examination		X	X	X	X	X	
MSFC ⁸		X	X	X	X	X	X
EDSS ⁸		X	X	X	X	X	X
MRI		X		X		X	
Pregnancy Test ²	X						
Immune Parameters Measurement		X	X	X	X	X	
Clinical Laboratory Tests ³	X	X				X	
Pre-study/Concomitant MedicationsMRI	X	XX	X	XX	X	XX	
Adverse Events	X	X	X	X	X	X	
Randomization to ECP ^{5,6} vs IVMP ⁷	X						

¹ Including history of MS, progression from RRMS to onset of SPMS. A complete history at start of study and interim history at each visit.

²For women of childbearing potential.

³ Both at screening and prior to each ECP procedure, a small amount of blood (2-4 teaspoons) will be drawn to evaluate CBC and chemistries.

⁴Subjects will be randomized at a 1:1 ratio to either ECP.or IVMP

⁵Patients should have ECP within 14 days of baseline visit.

⁶The frequency of ECP treatments will be:

Weeks 1-8: 3 x/ week

Weeks 9-16: 2x/week

Weeks 17-36: 2x/2 weeks

Weeks 37-43: 1x / every 2 weeks

Weeks 44-52: 1x/ every 4 Weeks

⁷ Corticosteroid is administered on a pulse basis and consists of 1 gram of methylprednisolone I.V. every 4 Weeks for 52 Weeks.

⁸These test will occur every three month through 2 years.

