5. PATIENT WITHDRAWAL AND REPLACEMENT

Patients may withdraw from the study at any time without penalty and for any reason without prejudice to his or her future medical care.

Patients must be withdrawn under the following circumstances:

- The patient withdraws consent
- Pregnancy (see Section 8.2.2.9)
- Unacceptable toxicity including patients on corticosteroids who develop psychosis or aseptic necrosis of the femoral head

Patients may be required to withdraw after discussion with the investigator for the following reasons:

- AE(s)
- At the discretion of the investigator
- Violation of eligibility criteria
- Deviation from the treatment plan specified in the protocol (e.g., incorrect administration of the study drug, failure to attend study visits, etc.)
- The treating physician can withdraw the patient from the study at any time and for any medical reason that he/she deems necessary
- The patient has a right to withdraw at any time, for any medical or other reasons.
- Patients who experience a clinical relapse (defined as neurological event characterized by new or worsening symptoms lasting 48 hours after a stable period of at least 30 days and is considered in the judgment of the investigator to be a clinical relapse). Patients who fail therapy will be off study, and further therapy will be at the discretion of the treating neurologist. The study will not cover any form of therapy after the patient is off study.
- Patients who have interval accumulation of T1 or T2 lesions and/ or gadolinium enhancing T1 lesions on the month 6 MRI scan
- In all cases, the reason(s) for withdrawal, and the primary reason, must be recorded on the case report form (CRF) or similar.

Withdrawn patients will be replaced.

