9.2.2 Screening

- If patient has had an appt with a physical exam in the last 30 days, that can be used for this screen.
- Obtain written informed consent.
- Verify inclusion and exclusion criteria
- Demographics and medical history
- MS Scoring and History
- Pregnancy test (for women of child-bearing potential patients only), whether to be done on urine or blood will be at investigator's discretion or per institutional practice.
- Collect blood sample for laboratory assessment (Table 1) (note: samples will be sent to local laboratories)
- Record pre-study/concomitant medication
- Randomization 1:1

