9.2.3 Baseline (Week 1)

A baseline visit should be performed and 1st ECP scheduled within 14days.

- Physical examination.
- Interim History
- Vital signs.
- MSFC
- MRI
- EDSS
- Blood for immune parameters (sent to the University of Michigan Neuroimmunology Research Laboratory)
- Collect blood sample for laboratory assessment (Table 1)
- Record concomitant medication.
- Assessment of pre-treatment events (AEs occurring from ICF signed to baseline visit).
- Start ECP within 14 days of baseline as defined in the schedule of assessments

9.2.4 Month 3/Week 12

- At this point patients who are assigned to ECP arm will have been tapered from 3 treatments weekly to two treatments weekly.
- Patients randomized to the ECP arm must receive their first ECP treatment within 14 days of baseline visit.
- Before ECP, on each day of treatment, blood samples will be collected for CBC or other clinical routine testing as needed, and no less that weekly.
- Patients admitted to the corticosteroid arm will receive a treatment once every month as stated above

- The following will also be performed at this time point: Interim history, vital signs, physical exam.
- Blood for immune parameters (sent to the UM Neuroimmunology Research Laboratory)
- MSFC
- EDSS
- Adverse Events
- Concomitant Medications

9.2.5 Month 6/Week 24

At this point patients on ECP will have been tapered to two treatments (on 2 consecutive days) every 2 weeks. If preferred, patients may be given the option of receiving one weekly treatment (as opposed to two treatments on 2 consecutive days) a schedule modification

- Before ECP on each day of treatment blood samples will be collected for the laboratory tests on Table 1 and sent to the University of Michigan Clinical Laboratory
- Patients admitted to the corticosteroid arm will receive a treatment once every month as stated above
- The following will also be performed at this time point:
 - Interim history, vital signs, physical exam.
 - Blood for immune parameters (sent to the UM Neuroimmunology Research Laboratory)
 - MSFC
 - EDSS
 - Adverse Events
 - Concomitant Medications
 - MRI with Gadolinium

9.2.6 Month 9/Week 36

On weeks 37-43, ECP-treated patients transition to one treatment every two weeks and for Patients admitted to the corticosteroid arm will receive a treatment once every month

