11.9 Duration of the Study

For an individual patient, the maximum duration of the study for each patient will be up to 52 weeks (excluding up to 1 week screening). The total study is expected to last 2 years.

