Pregnancy: Methoxsalen may cause fetal harm when given to a pregnant woman. Doses of 80 to 160 mg/kg/day given during organogenesis caused significant fetal toxicity in rats. The lowest of these doses, 80 mg/kg/day, is over 4000 times greater than a single dose of UVADEX[®] on a mg/m² basis. Fetal toxicity was associated with significant maternal weight loss, anorexia and increased relative liver weight. Signs of fetal toxicity included increased fetal mortality, increased resorptions, late fetal death, fewer fetuses per litter, and decreased fetal weight. Methoxsalen caused an increase in skeletal malformation and variations at doses of 80 mg/kg/day and above. There are no adequate and well-controlled studies of methoxsalen in pregnant women. If UVADEX[®] is used during pregnancy, or if the patient becomes pregnant while receiving UVADEX[®], the patient should be apprised of the potential hazard to the fetus. Women of childbearing potential should be advised to avoid becoming pregnant.

PRECAUTIONS

General: *ACTINIC DEGENERATION:*

After methoxsalen administration, exposure to sunlight and/or ultraviolet radiation may result in "premature aging" of the skin.

BASAL CELL CARCINOMAS:

Patients exhibiting multiple basal cell carcinomas or having a history of basal cell carcinomas should be diligently observed and treated.

SKIN BURNING:

Serious burns from either UVA or sunlight (even through window glass) can result if the recommended dosage of methoxsalen is exceeded or precautions not followed.

THE FORMATION OF CATARACTS:

Exposure to large doses of UVA light causes cataracts in animals. Oral methoxsalen exacerbates this toxicity. The concentration of methoxsalen in the human lens is proportional to the concentration in serum. Serum methoxsalen concentrations are substantially lower after extracorporeal UVADEX[®] treatment than after oral methoxsalen treatment. Nevertheless, if the lens is exposed to UVA light while methoxsalen is present, photoactivation of the drug may cause adducts to bind to biomolecules within the lens. If the lens is shielded from UVA light, the methoxsalen will diffuse out of the lens in about 24 hours.

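### The only scheduled pregnancy test is at screening, with none at baseline or during 52 weeks of treatment, although pregnancy is an exclusion and a mandatory reason for withdrawal

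*Combined protocol and SAP*

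**What the plan says.** **Testing.** In Table 2 (Section 9.1) the row "Pregnancy Test" is marked only under "Screening (-30days"; a footnote limits it to women of childbearing potential. Section 9.2.2 lists the same item: "Pregnancy test (for women of child-bearing potential patients only". The lists for baseline, months 3, 6 and 9, and Week 52 onward (9.2.3 to 9.2.7) do not repeat it. The early termination visit (9.2.8) only points to the Week 52 assessments, and Table 1, the laboratory panel in 8.2.3, has no pregnancy test.

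**Rules that depend on pregnancy status.** Pregnancy is exclusion 12 in Section 4.2. In Section 5 it is one of three circumstances in which a patient must be withdrawn: "Pregnancy (see Section 8.2.2.9". Section 8.2.2.8 sets out how pregnancies are reported and followed up.

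**Hazard.** For methoxsalen, Appendix 4 states: "Methoxsalen may cause fetal harm when given to a pregnant woman". It assigns Pregnancy Category D. For corticosteroids, Appendix 3 (13.3.2) gives no category and asks only that benefit be weighed against hazard.

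**Timing.** On the start of ECP, Section 9.2.3 says: "A baseline visit should be performed and 1st ECP scheduled within 14days". Section 9.2.4 says: "Patients randomized to the ECP arm must receive their first ECP treatment within 14 days of baseline visit". Footnote 5 of Table 2 also gives 14 days, but Sections 3.1 and 10.1 give 5 days. On screening, Table 2 shows 30 days, whereas Section 11.9 describes the patient's time on study as "excluding up to 1 week screening".

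**The concern.** The plan names a risk, excludes women who carry it and requires withdrawal if it arises, but schedules no test after screening that would tell the investigator it has arisen. Two gaps follow.

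- **Before treatment.** A woman who conceives between screening and her first session starts treatment with a negative result on file.
- **During treatment.** A pregnancy comes to light only if the patient reports it or someone suspects it.

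At stake is avoidable fetal exposure to a hazard that the protocol's own appendix describes. The primary analysis is not threatened.

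**Working it through.** The plan states no interval from test to exposure, so there is no figure to reproduce. The interval follows from its windows.

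**Longest gap from test to first ECP = screening window + window from baseline to first ECP.** Table 2 does not say what its 30 days are counted from; they are read here as days before baseline.

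| Screening window | Start window | Longest gap |
|---|---|---|
| 30 days (Table 2) | 14 days (Table 2 footnote 5; 9.2.3; 9.2.4) | 30 + 14 = 44 days |
| 30 days (Table 2) | 5 days (3.1; 10.1) | 30 + 5 = 35 days |
| 7 days (11.9) | 14 days | 7 + 14 = 21 days |
| 7 days (11.9) | 5 days | 7 + 5 = 12 days |

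Under all four readings, no scheduled test falls between screening and first exposure. The documents do not give the time to the first methylprednisolone pulse, so the same gap cannot be computed for the control arm.

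**Treatments given with no scheduled test.** From the schedule in Table 2:

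- Weeks 1-8: 8 × 3 = 24
- Weeks 9-16: 8 × 2 = 16
- Weeks 17-36: 20 (two per 2 weeks for 20 weeks)
- Weeks 37-43: 3 to 4
- Weeks 44-52: 2 to 3

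The total is 65 to 67 ECP sessions. The control arm receives about 52 / 4 = 13 pulses. Scheduled pregnancy tests between first treatment and Week 52: 0 in either arm.

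**What added tests would achieve.**

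- With a baseline test, the longest gap to first ECP is the start window alone: 14 or 5 days, in place of 12 to 44.
- With repeats at months 3, 6 and 9 (Weeks 12, 24 and 36), the nominal untested stretches up to Week 52 are 12, 12, 12 and 16 weeks.
- The repeats limit exposure but do not prevent it. A conception just after the baseline test could still meet 24 + (4 × 2) = 32 sessions by Week 12.

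**Cross-reference.** Section 5 sends the reader to 8.2.2.9 for pregnancy. That section covers complaints and device malfunctions; pregnancy is 8.2.2.8.

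**The case against.** A reader might infer that the withdrawal rule cannot work in time. The documents do not support that. Section 5 does not tie withdrawal to a test. Section 4.1 asks for willingness to use contraception throughout, an interim history is taken at each visit (8.2.6), and ECP patients attend three times a week at first, with other routine testing allowed as needed (9.2.4). Any of these could bring a pregnancy to light. Against that, none of the visit lists names a contraception check, and neither the interim history nor the as-needed testing mentions pregnancy. The rule can operate, but without a scheduled trigger.

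A reader might also take 44 days as the plan's gap. It is the longest of four readings and needs both the 30-day and the 14-day windows.

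A third tempting step is to assume a pregnancy unnoticed through all 24 sessions of weeks 1-8. With conception just after screening and the longest gap, that means about 44 + 56 = 100 days without suspicion; with the 12-day gap it means 12 + 56 = 68 days. Nothing in the documents says how likely this is, so the point does not rest on it.

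The label also tempers the hazard. It asks for no pregnancy testing, only that women be advised to avoid pregnancy and told of the hazard if it occurs. It puts the lowest fetotoxic rat dose at over 4000 times a single UVADEX dose, and Section 7.1.1 calls systemic exposure minimal. Category D concerns methoxsalen, hence the ECP arm only. This lowers the likely harm. It does not explain why the plan excludes and withdraws for pregnancy yet stops testing for it at screening.

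**Conclusion.** The point holds as a gap in the assessment schedule. One pregnancy test is scheduled, at screening, and none at baseline or over 52 weeks of treatment. After screening, detection relies on patient report or clinical suspicion, and no scheduled test covers the interval from screening to first treatment. For ECP that interval can reach 12, 21, 35 or 44 days because the plan's own windows conflict. The two upper figures assume that the 30 days run to baseline.

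The label's specific warning applies to the ECP arm; for corticosteroids the documents support only a weighing of benefit against hazard. The number of women of childbearing potential among the 66 planned subjects is not given (ages 18 to 75 are eligible), so the expected number of affected pregnancies cannot be estimated. This is a cheap improvement in safety monitoring that the sponsor should make. It has no bearing on the validity of the efficacy comparison.

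**What to change.** 1. In Table 2 and Section 9.2.3, add a pregnancy test for women of childbearing potential at the baseline visit, with the result known before first treatment. This test matters most, because it checks exclusion 12 close to exposure.
2. Repeat it at months 3, 6 and 9 (9.2.4 to 9.2.6) and record the result on the CRF, so that the existing Section 5 rule has a scheduled trigger. A month-12 test is not needed for this purpose, since treatment is then ending.
3. Use urine or a clinical-laboratory sample. The immune-parameter blood goes to a research laboratory, and Table 2 marks no clinical laboratory tests at months 3, 6 or 9, so urine is simplest in both arms. Section 9.2.2 already allows urine or blood.
4. Reconcile the screening window (Table 2 against 11.9) and the time from baseline to first ECP (Table 2, 9.2.3 and 9.2.4 against 3.1 and 10.1), and state what the 30 days are counted from.
5. Correct the Section 5 cross-reference from 8.2.2.9 to 8.2.2.8.

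The cost is four inexpensive tests per woman of childbearing potential and a Table 2 amendment, with no added visit. One consequence needs a sentence in the plan. Table 2 and 9.2.2 place randomization at screening, so a positive baseline test would come after randomization. Section 10.2.1 counts withdrawn patients as non-responders and Section 5 replaces them; the plan should say how such a woman is counted.

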6.2 Study Arm: Extracorporeal Photopheresis

ECP will administered according to the following schedule:

Study Arm: Weeks 1-8: 3 times per week

Weeks 9-16: Twice per week

Weeks 17-36: Treatment on two consecutive days every 2 weeks (or optionally, one treatment per week)

Weeks 37-43: Once every 2 weeks

Weeks 44-52: Once every 4 Weeks

The CELLEX[®] System are integrated photopheresis systems that are approved in US and Europe, and marked specifically to perform photopheresis. With the CELLEX[®] System, whole blood is drawn from the patient, centrifuged and separated into its components: plasma, white blood cells, and red blood cells. The white blood cells and a portion of the plasma are collected in a separate chamber for treatment. The remaining plasma and red blood cells are returned to the patient untreated. This collection process is repeated over several cycles. The buffy coat suspension of white blood cells is then exposed to a predetermined amount of UVA light (photo activation) after being inoculated with UVADEX[®] (methoxsalen) Sterile Solution. Following the photo activation of the buffy coat suspension, the treated cells are returned to the patient.

Every attempt should be made to process 1500-2000 mL of blood during each treatment.

UVADEX[®] (methoxsalen) Sterile Solution is supplied in a 10 mL single-use vial. Each mL of solution contains 20 mcg of UVADEX[®] (methoxsalen) Sterile Solution. Each vial contains 10 mL of UVADEX[®] (methoxsalen) Sterile Solution, which is more drug than necessary for most treatments. However, the vials are designed for a single use. Therefore, there will be surplus of drug remaining in the vial at the conclusion of each treatment. Study center staff should NOT attempt to reuse any portion of this unused study drug once the seal has been compromised. The remaining UVADEX[®] (methoxsalen) Sterile Solution should be discarded after verification of dose by the study monitor as per study reference manual.

In the ECP process, UVADEX[®] (methoxsalen) Sterile Solution will be injected directly into the Recirculation Bag of the extracorporeal circuit after completion of the buffy coat collection, just prior to initiating photo activation. The dose of UVADEX[®] (methoxsalen) Sterile Solution used to inoculate these cells will be calculated based on the treatment volume collected during the plasma/buffy coat collection process, using the following formula:

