8.2.2.4 Recording Adverse Events

Adverse event reporting will extend from signing of informed consent until completion of study (Week 52) or 30 days after the last study intervention. Adverse events occurring after the end of the study should be reported to the Sponsor by the investigator if the investigator considers there is a causal relationship with the study treatment.

All AEs (including AEs resulting from active standard of care medication and study instrument), regardless of the relationship to study drug, will be recorded in the CRF.

In addition, the technician performing the ECP procedure will observe and record any AEs that occur during the procedure. Treatment will be stopped if the patient cannot tolerate the procedure.

All AE reports should contain a brief description of the event, date of onset, date of resolution, intensity, treatment required, relationship to study drug, action taken with the study drug, outcome, and whether the event is classified as serious.

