8.2.3 Laboratory Parameters

Clinical laboratory assessments will be performed by the UM Hospital Clinical Laboratory at the University of Michigan. Research laboratory studies to measure immunological parameters will be conducted the Neuroimmunology Research Laboratory in the Department of Neurology at the University of Michigan ([name], Director).

Blood samples should be taken using standard venipuncture techniques. Blood samples should be processed according to the procedure described in the laboratory manual.

Laboratory parameters will be determined in accordance with the Schedule of Assessments on Table 2.

Table 1: Laboratory Assessments

Hematology:	Complete CBC
Chemistry:	Creatinine Glucose Triglycerides Urea Uric acid Bilirubin Cholesterol Sodium Potassium
Liver Function Tests	Alkaline phosphatase Aspartate transaminase Alanine transaminase
Immune Parameters	Myelin basic protein –specific IFN γ or IL-17 producing PBMC, Frequency of tetanus toxoid –specific IFN γ or IL-17 producing PBMC, plasma levels of IFN γ , IL-17, IL-4, IL-10, IL-12, IL-21, IL- 23, CCL2, GRO α , CXCL8, CXCL10, CCL11, CXCL13, GM-CSF, G-CSF and neutrophil elastase

Clinically significant laboratory abnormalities should be recorded as AEs according to investigator's judgment. The maximum total amount of blood that will be taken during the study from an individual patient for research studies is 60 ml per blood draw. There will be a total of five blood draws, separated by intervals of 9 weeks or longer. Patients on ECP will have an additional blood draw of 5 ccs prior to every procedure to determine hematocrit and platelet count.

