10.2.2 Analysis of Secondary Endpoints

The secondary endpoints include:

- Change in Plasma levels of Immunological Factors and Frequencies of IFN γ and IL-17 MBP-specific PBMC at months 3, 6, 9 and 12 compared with baseline
- MSFC 3 dimensional composite z-score at every 3 month time point through 2 years compared to baseline
- Expanded Disability Status Scale (EDSS) score at every 3 month time point through 2 years compared to baseline
- Percentage of subjects with improvement (as defined for the primary endpoint) at months 3, 6, 9 and 12 compared to baseline
- Occurrence of clinical relapse at any point in the study

- Interval change in T2 lesion number and volume on MRI scans obtained at months 6 and 12 compared to baseline
- The number and volume of gadolinium enhancing lesions on MRI scans obtained at months 6 and 12 compared to baseline
- Interval change in the number and volume of gadolinium enhancing lesions on MRI scans obtained at months 6 and 12 compared to baseline.
- Toxicity and Adverse events in both arms

For continuous outcomes, two-sample t-tests or Wilcoxon rank sum tests will be used to compare the treatment arms. For categorical outcomes, Chi-square tests or Fisher's exact test will be used to compare the treatment arms. The proportion of subjects who experience adverse events and serious adverse events will be summarized by treatment group descriptively; no inferential tests will be performed.

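### Pre-ECP blood tests give the ECP arm about 67 scheduled safety draws after baseline against one for controls, so the by-arm AE proportions lean toward more laboratory AEs with ECP, by an amount the documents do not fix

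*Combined protocol and SAP*

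**What the plan says.** - **Common testing.** Table 2 (section 9.1) schedules clinical laboratory tests at screening, baseline and month 12 for all subjects. Only the month 12 test falls after treatment starts.
- **Extra testing with ECP.** Footnote 3 to Table 2 states that "prior to each ECP procedure, a small amount of blood (2-4 teaspoons) will be drawn to evaluate CBC and chemistries". Section 8.2.3 instead describes an "additional blood draw of 5 ccs prior to every procedure" and names only hematocrit and platelet count. The month 3 text in 9.2 asks for a CBC or other routine tests as needed. The month 6, month 9 and week 52 texts ask for the Table 1 tests.
- **Controls.** Infusions are given every 4 weeks (6.1), with no laboratory test attached. The week 52 list in 9.2.7 mentions Table 1 tests only before ECP, so the control draw at month 12 rests on Table 2 alone.
- **From laboratory finding to AE.** Section 8.2.3 says: "Clinically significant laboratory abnormalities should be recorded as AEs". It leaves this to investigator judgment and sets no grade or threshold.
- **Extra observation.** In 8.2.2.4, "the technician performing the ECP procedure will observe and record any AEs that occur during the procedure".
- **Analysis.** In 10.2.2, "The proportion of subjects who experience adverse events and serious adverse events will be summarized by treatment group descriptively", without inferential tests. Section 10.3 puts laboratory results and AEs into line listings by arm. Neither section mentions testing frequency.

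**The concern.** How often a patient is tested affects how many abnormalities are found. Here the frequency differs greatly between arms because of the treatment procedure itself. A transient abnormality has many chances of being seen in an ECP patient and almost none in a control. Each one judged clinically significant enters the AE count.

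Comparing the safety and tolerability of the two treatments is a secondary objective (2.2). A reader who sees a higher AE proportion with ECP could not tell whether it reflects the treatment or the testing. The absence of a significance test does not help, because the two proportions will still be read against each other.

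The imbalance can also hide real effects in controls. Appendix 3 (13.3.1) lists potassium loss, transaminase increases and reduced carbohydrate tolerance as corticosteroid effects. Table 1 includes potassium, the transaminases and glucose. Controls have no scheduled test of these between baseline and month 12.

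**Working it through.** The documents give no total of sessions or draws, so there is no stated figure to reproduce.

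**1. Sessions, from the schedule in 6.2 and the synopsis**
- "Weeks 1-8: 3 times per week": 8 × 3 = 24
- "Weeks 9-16: Twice per week": 8 × 2 = 16
- "Weeks 17-36: Treatment on two consecutive days every 2 weeks": 10 × 2 = 20 (the weekly option also gives 20)
- Last two blocks in the synopsis (weeks 37-44 and 45-52): 8/2 + 8/4 = 4 + 2 = 6

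The synopsis total is 24 + 16 + 20 + 6 = 66. The body text divides the last two blocks as weeks 37-43 and 44-52, giving 3 or 4 plus 2 or 3 sessions, so 65 to 67 in all. The two versions should be reconciled, but the difference does not matter here.

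**2. Scheduled safety draws after baseline**
- ECP: 66 + 1 (month 12) = 67
- Control: 1 (month 12)

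**3. Equal risk at every draw.** Let p be the chance that a draw yields a recordable abnormality, the same in both arms and independent between draws. The documents give no p, so a range is assumed. The share of patients with at least one is 1 − (1 − p)^67 with ECP and p in controls. Expected counts are 33 times these shares.

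| p per draw | ECP share | Control share | Expected patients, ECP vs control (of 33 each) | Chance that ECP count is higher |
|---|---|---|---|---|
| 0.01% | 0.7% | 0.01% | 0.2 vs 0.0 | 20% |
| 0.1% | 6.5% | 0.1% | 2.1 vs 0.03 | 88% |
| 0.5% | 28.5% | 0.5% | 9.4 vs 0.2 | >99% |
| 1% | 49.0% | 1.0% | 16.2 vs 0.3 | >99% |
| 5% | 96.8% | 5.0% | 31.9 vs 1.7 | >99% |

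**4. Equal risk, one episode per affected patient.** This model avoids independence between draws. It assumes that 20% of patients in each arm (0.20 × 33 = 6.6) have one episode of fixed length, with onset uniform over 364 days. Controls are detected only if the episode spans day 364, so their share is (length in days)/364. The ECP share was simulated on the 66-session calendar plus day 364.

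| Episode length | Seen, ECP | Seen, control | Expected patients, ECP vs control |
|---|---|---|---|
| 7 days | 64% | 2% | 4.2 vs 0.1 |
| 28 days | 100% | 8% | 6.6 vs 0.5 |
| 90 days | 100% | 25% | 6.6 vs 1.6 |
| 180 days | 100% | 49% | 6.6 vs 3.3 |
| Lasting to month 12 | 100% | 100% | 6.6 vs 6.6 |

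**5. Dilution in the planned table.** Section 10.2.2 counts subjects with any AE. If a share q of each arm has some other AE, independently of laboratory findings, the excess in the overall proportion is (1 − q) × (ECP share − control share). At p = 0.5% the laboratory excess is 28.5% − 0.5% = 28.0 percentage points. With q = 80% (assumed) it becomes 0.2 × 28.0 = 5.6 points, and with q = 90% it becomes 2.8.

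**6. Which tests are affected.** If 8.2.3 governs, only hematocrit and platelets are tested more often. Chemistry and liver tests would then be on the same three-visit schedule in both arms, and the imbalance for them would vanish.

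**7. The draw itself.** At 5 mL per teaspoon, 2-4 teaspoons is 10-20 mL. Over 66 sessions, 8.2.3 gives 66 × 5 = 330 mL and footnote 3 gives 660 to 1,320 mL. This is a separate inconsistency and is not evidence of bias.

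**The case against.** A reader might infer that the tables are bound to show an excess of laboratory events with ECP, even if there are none. The documents do not support that. If no abnormalities occur, extra testing finds none. At 0.01% per draw the ECP count is the higher one in only about 20% of trials, and abnormalities lasting to month 12 are found equally. Investigator judgment also filters isolated findings, and repeated draws days apart in one patient are not independent as step 3 assumes.

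The planned summary is of any AE and any SAE, not of laboratory AEs, so step 5 applies. Other AE capture is shared. Both arms have AE review at months 3, 6, 9 and 12, spontaneous reports and open questioning, the same reporting window, and controls attend every 4 weeks for infusion. Laboratory events that cause symptoms can therefore surface in either arm. No test is distorted, because none is planned.

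These points limit the size and certainty. They leave the direction standing, because none of the shared routes detects a silent abnormality in a control between baseline and month 12.

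A reader might also infer that events recorded by the technician during ECP should leave the between-arm comparison. They should not. Section 7.1.1 lists venous access complications and transient hypotension as effects of the procedure. Removing such events would hide real harms and tilt the summary toward ECP.

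**Conclusion.** The concern holds as a bias of known direction and unknown size. With about 67 scheduled post-baseline draws against one, equal true risk leads on average to more detected laboratory AEs with ECP unless abnormalities persist to month 12. This assumes that controls have no routine tests beyond those scheduled and that investigators apply the same judgment in both arms.

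The expected excess ranges from negligible to most of the arm over the assumed rates, and the documents give nothing to narrow it. It shrinks in the overall any-AE proportion and is limited to hematology if 8.2.3 describes the draw. It affects interpretation of a descriptive safety summary and not the primary analysis. It merits a cheap improvement to the displays, plus reconciliation of the draw descriptions.

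**What to change.** **In 10.2.2 and 10.3**
- Keep the overall AE and SAE summary with all events in both arms, including those observed during the procedure.
- Add a separate display of laboratory AEs comparing the arms at month 12, the one on-treatment laboratory visit they share, with baseline as reference.
- Show laboratory AEs found only at pre-ECP draws as their own row, and give the number of draws per arm.

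**Elsewhere**
- Reconcile the volume and test list of the pre-ECP draw across 8.2.3, footnote 3 to Table 2, the month 3 text in 9.2 and the later visits in 9.2.
- List the month 12 clinical laboratory draw for controls in 9.2.7, to match Table 2.

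**Cost.** Wording and table programming, with no extra tests and no safety data discarded. The downside is that the like-for-like laboratory comparison rests on a single on-treatment time point and can miss transient abnormalities in either arm. That is why the full summary and the pre-ECP row must stay beside it.
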